#### **4.4.4. Other Endpoints**

The primary population for the analysis of the bone formation marker, s-PINP, and the bone resorption marker, s-CTX, will be the mITT population. The same analyses will be repeated for the ITT and PP populations. Analysis of these bone turnover markers will be based on the ratio of the post-baseline value relative to the baseline value at each visit (using the analysis visit windows defined in [Table 3](#)). The transformation of the loge ratio of post-baseline versus baseline value (derived by dividing the post-baseline value by the baseline value and then applying the natural log transformation) will be used to normalize the distributions of the s-PINP and s-CTX parameters. The analysis comparing abaloparatide-sMTS with abaloparatide-SC will use a MMRM model similar to the MMRM model for BMD analysis, with the appropriate natural-log transformed baseline bone turnover marker value as covariate. The analysis will be repeated based on the nominal visits.

Geometric mean ( $\pm$ SE) values, geometric mean values ( $\pm$ SE) relative to baseline, mean ( $\pm$ SD) change from baseline values, and mean ( $\pm$ SD) percent change from baseline values at each visit for s-PINP and s-CTX will be tabulated using descriptive statistics.

Plots will be presented for the geometric mean ( $\pm$ SE) of the ratio relative to baseline, as well as mean ( $\pm$ SE) percent changes from baseline, for s-PINP and s-CTX values over time by treatment group. Plots will also be presented for the median ( $\pm$  interquartile range) for the raw values of s-PINP and s-CTX over time by treatment group.

Any value of s-PINP or s-CTX that is provided as “*< numeric value*” or “*> numeric value*” will be imputed as the *numeric value* in all summary tables and analyses, but will be shown with the actual result in the listings.

#### **4.4.5. Exploratory Efficacy Endpoints**

Analysis of the exploratory efficacy endpoints described in this section will be performed using the mITT population as the primary analysis and repeated for the ITT and PP populations.

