4.3. Subject Withdrawal or Termination

4.3.1. Reasons for Withdrawal or Termination

Subjects will be informed that they have the right to withdraw from the study at any time for any reason without prejudice to their medical care.

Subjects who withdraw consent prior to being randomized into the study will be recorded as having failed the eligibility criterion for study consent (signed ICF is no longer valid at the time of randomization).

The Investigator may consider terminating study drug and/or discontinuing subjects from the study for the following reasons:

• Continuing significant deterioration from baseline (≥7%) of BMD at spine or hip (after confirmation of the finding)

 Hypercalcemia, hypercalciuria, or excessive skin reactions as described in Section 4.7

- Severe hypersensitivity to abaloparatide or test materials
- Refusal of treatment
- Inability to complete study procedures
- Lost to follow-up
- SAEs (as described in Section 7.1.2)
- A complex of AEs or laboratory abnormalities which, in the judgment of the Investigator, justifies treatment cessation
- Serious intercurrent illness
- Noncompliance
- Protocol deviations
- Administrative reasons
- Incident vertebral or nonvertebral fragility fracture

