6.2.7. Treatment Period

Subjects who remain eligible for study participation will be randomly allocated to a treatment group through the IRT, using a 1:1 randomization ratio on Day 1 to receive treatment with either abaloparatide-SC 80 μ g per day or daily 300 μ g abaloparatide-sMTS administration. During the Treatment Period, subjects will self-administer a single dose of study drug once a day. Subjects will also take calcium and vitamin D each day during the Treatment Period, as directed by the Investigator.

Subjects will be randomized on Day 1 of the Treatment Period. During the Treatment Period, subjects will self-administer study drug once a day for 12 months and visit the study site as shown in Table 1.

At each study site visit during this period, as indicated in Table 1, recent health status will be obtained, the diary reviewed, AEs collected, and orthostatic blood pressure and vital signs performed. Laboratory assessments of chemistry, hematology, and urinalysis will be obtained at Day 1, Month 1, Month 6, and Month 12 and a 24-hour urine collection will start on the day prior to Day 1 and on the day prior to the Month 3 visit. Clinical assessments for fracture will be performed at the pretreatment visit and at Day 1 and Months 1, 3, 6, 9, and 12. Source documentation (imaging report and/or film along with other supporting documentation as appropriate) will be collected from each site to confirm fracture.

Subjects will have BMD assessed by DXA at the lumbar spine, total hip, and femoral neck at Screening and Months 3, 6, and 12. All DXA assessments will be performed by a central imaging laboratory. Bone turnover marker assessments (s-PINP and s-CTX) will be performed on Day 1 and Months 1, 3, 6, and 12.

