6.7. Discontinuation from the Study

Subjects may voluntarily discontinue from the study for any reason at any time.

Any subject who demonstrates decreases in BMD \geq 7% from baseline of this study at the lumbar spine or total hip will have the assessment repeated and, if confirmed, will be notified by the Investigator and may be withdrawn from the study. Subjects sustaining a radiologically confirmed incident vertebral or nonvertebral fracture will be informed of the finding and will be counseled as to treatment options and may discontinue or choose to remain on the study.

Subjects who decide they do not wish to participate in the study further should be encouraged to return for the assessments indicated for the Month 12/EOT Visit and 1 month later for the Follow-up/EOS Visit in the Schedule of Assessments and Procedures (Table 1). If they fail to return for these assessments for unknown reasons, every effort (eg, telephone, email, and letter) should be made to contact them to obtain final follow-up information.

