## **2. SUBJECT ANALYSIS POPULATIONS**

### **2.1. Population Definitions**

Five subject populations will be considered in the statistical analyses of this study.

- Intention-to-Treat (ITT) population**

The ITT population consists of all subjects randomized into this study.

- Modified Intention-to-Treat (mITT) population**

The mITT population includes all randomized subjects who received at least one dose of study drug and had a baseline lumbar spine BMD measurement and at least one post-baseline lumbar spine BMD measurement.

- Safety population**

The Safety population consists of all randomized subjects who received at least one dose of study drug.

- Per-Protocol (PP) population**

The PP population consists of all mITT subjects who did not have any critical protocol deviations (described in [Section 2.2](#)).

- Antibody Population**

The Antibody population will include subjects in the Safety population who have at least one post-baseline anti-drug antibody assessment.

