#### **4.4.5.2. Time to Clinical Fracture**

Analysis of the time to new clinical fracture by Month 12 will be performed for exploratory purposes. Duration in days from the date of randomization to the first incidence of clinical fracture will be derived.

The crude incidence rates, Kaplan-Meier estimates of the incidence rate at Month 12, hazard ratio (95% CI) based on a Cox proportional hazard model without covariates, and Kaplan-Meier curves, and p-values from the log-rank test for the comparison of the treatment groups will be generated for this time-to-event variable.

If a subject does not experience any clinical fracture over the 12 months of treatment plus the 30-day follow-up, this subject will be censored at the last known day in the study up to the follow-up visit.

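### Time to clinical fracture starts at randomization, but its primary population (mITT) requires a later spine scan, and its risk period runs past Month 12 (minor)

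*SAP*

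**What the plan says.** **Population.** SAP Section 4.4.5 sets one rule for all exploratory efficacy endpoints: the analyses "will be performed using the mITT population as the primary analysis and repeated for the ITT and PP populations". Under SAP Section 2.1, mITT members received at least one dose and "had a baseline lumbar spine BMD measurement and at least one post-baseline lumbar spine BMD measurement". PP is a subset of mITT. By contrast, "The ITT population consists of all subjects randomized into this study".

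**Clock.** SAP Section 4.4.5.2 describes the endpoint as new clinical fracture by Month 12 and adds: "Duration in days from the date of randomization to the first incidence of clinical fracture will be derived". A woman with no fracture over treatment plus the 30-day follow-up is censored at her last known day, up to the follow-up visit. Crude incidence, the Kaplan-Meier estimate at Month 12, a Cox hazard ratio and a log-rank test are planned.

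**Schedule.** Protocol Section 6.2.7 places DXA "at Screening and Months 3, 6, and 12". Of fractures it says: "Clinical assessments for fracture will be performed at the pretreatment visit and at Day 1 and Months 1, 3, 6, 9, and 12".

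**Leaving after a fracture.** Protocol Section 4.3.1 lists "Incident vertebral or nonvertebral fragility fracture" among the reasons an investigator may consider for stopping drug or study. Under Protocol Section 6.7, a woman with a confirmed fracture "may discontinue or choose to remain on the study". Protocol Section 4.3.2 asks that women who leave early be encouraged to complete the end-of-treatment procedures, which include DXA, but does not require it.

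**The concern.** For the BMD models, requiring a post-baseline scan costs little, because a woman without one has no outcome to contribute. Fracture is different: it needs no scan, it is assessed from Day 1, and the plan's own censoring rule already handles women who leave early. Requiring a scan therefore makes membership of the fracture risk set depend on something that happens after randomization, and the event itself can be the reason the scan never happens. No text restores a fractured woman without a scan to the mITT analysis.

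At stake is the only comparative fracture analysis in the plan. The trial is open-label, patch against injection, so early leaving could differ between arms. With few events expected, a small imbalance in who is dropped can move the hazard ratio.

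The second part is a mismatch of time frame. The endpoint is fracture by Month 12, but the risk period runs through the follow-up month, after the scheduled clinical assessment of new fractures has ended.

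**Working it through.** **1. The plan's own figures.** No sample size or event count is stated for fracture. The figures available are those for the primary endpoint (SAP Section 3.1): margin 2.0, SD 6.35, true difference 0, one-sided 0.025, power 90%.
- n per arm = 2 × (1.96 + 1.2816)² × 6.35² / 2.0² = 211.8, so 212 per arm and 424 in total, against 426 stated.
- 426 / (1 − 0.10) = 473.3, rounded up to 474, as stated.

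**2. Women expected outside mITT.** 474 − 426 = 48, or 48/474 = 10.1%; about 24 per arm.

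**3. Fracture risk (assumption).** The documents give no 12-month clinical fracture rate for this trial. Take 2% to 5% with a constant hazard, so that a quarter falls before Month 3.
- All events per arm: 237 × 0.02 = 4.7 to 237 × 0.05 = 11.9.
- Of these, before Month 3: 4.7/4 = 1.2 to 11.9/4 = 3.0.

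**4. Events lost from mITT.** Only events among women outside mITT are lost.
- Same hazard as the other women: 24 × 0.02 × 0.25 = 0.12 to 24 × 0.05 × 0.25 = 0.30 per arm.
- Wider range, both arms together: with a risk of 1% to 5%, the 48 women followed for 1.5 to 3 months before leaving, and a hazard equal to or three times that of the others, 0.06 to 1.8 events lie outside mITT. That is 1.4% to 7.8% of all events.
- Extreme for early fractures: if every fracture before Month 3 led to leaving with no scan, the loss would be the 1.2 to 3.0 per arm of step 3. This is a bound, not an expectation.

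**5. Sensitivity to one-sided loss.** Suppose each arm has 5 to 10 events and the true rate ratio is 1.0. Losing one event from one arm only gives 4/5 = 0.8 to 9/10 = 0.9; losing three gives 2/5 = 0.4 to 7/10 = 0.7. Step 4 shows that even one such loss exceeds the expected number unless fracture drives leaving.

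**6. Risk period.** Treatment is 12 × 30 = 360 days and follow-up adds 30, so 30/390 = 7.7% of the scheduled risk period lies beyond the endpoint. If that month were fully observed at the same hazard, it would add about 4.7/12 = 0.4 to 11.9/12 = 1.0 events per arm. It is observed less fully: the row for clinical assessment of new fractures in Protocol Table 1 ends at Month 12, and Visit 17 (Protocol Section 6.2.8) has a symptom-directed examination that covers potential vertebral fracture. A Kaplan-Meier estimate at Month 12 uses only data up to Month 12, so it does not change. Crude incidence, Cox and log-rank have no stated Month 12 cut-off, so they do.

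**The case against.** The strongest reply is that the plan already holds the remedy. The ITT repeat keeps every randomized woman and her event. The analysis is exploratory, was added by the SAP, and carries no decision rule. With an assumed 5 to 20 events in total and a hazard ratio of 0.5, the power of the log-rank comparison is only about 12% to 34%. All of this stands, and it limits the point to a minor one. It does not explain why the scan-dependent result should be the primary one for an outcome that needs no scan.

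Several stronger readings are tempting but not supported:
- **That early fractures disappear from the trial.** They do not. ITT keeps them. Protocol Section 7.1.4 exempts many fractures from adverse-event recording, but requires all of them in the eCRF, and SAP Section 3.11 puts all available data in listings.
- **That this is immortal-time bias.** A woman who fractures in Month 1 and is scanned later stays in mITT with her event, so no event-free interval is guaranteed. Early leavers without a fracture are dropped too, so the direction of bias is not known.
- **That the 1 to 3 early events per arm would all be lost.** Those are expected among all 237 women. A loss requires a fracture, an exit and no scan at all; a fracture does not force an exit, and any scan from Day 2 counts under SAP Table 3.
- **That nothing looks for fractures at follow-up.** Visit 17 does examine for potential vertebral fracture, and symptom-driven spinal imaging is allowed at any time. Ascertainment is narrower, not absent.

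**Conclusion.** The point holds as a minor one. In the mITT and PP fracture results, a woman who fractures and leaves without a post-baseline lumbar spine scan is removed together with her event; in the ITT repeat she is not. The expected loss is about 0.1 to 0.3 events per arm. This rests on the plan's 10% outside mITT, an assumed 12-month risk of 2% to 5%, a constant hazard and leaving unrelated to fracture. It is larger if fracture prompts leaving, and the documents do not allow that to be quantified. Differential leaving between arms is possible but not shown.

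The mismatch between the Month 12 endpoint and the 13-month risk period is real for crude incidence, Cox and log-rank, and absent for the Kaplan-Meier estimate at Month 12. Neither issue touches the primary non-inferiority conclusion on lumbar spine BMD.

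**What to change.** 1. In SAP Section 4.4.5, exempt Section 4.4.5.2 from the general rule: ITT is primary for time to clinical fracture, with mITT and PP supportive.
2. In SAP Section 4.4.5.2, for crude incidence, Cox and log-rank, count events and censor at the earlier of the last known day in the study and Month 12. Define Month 12 as the Month 12 visit, or Day 360 for women who stopped early. Do not use an early end-of-treatment visit as the cut-off: that would discard follow-up inside 12 months for exactly the women at issue, and would give no date for those who skip that visit.
3. List fractures after Month 12 separately.

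The cost is SAP wording and a small change to the event and censoring derivation. The ITT output is already planned, and no data collection changes.

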##### **4.4.5.1. BMD Responders**

Three categories of BMD response will be evaluated: % BMD increase  $> 0\%$ ,  $> 3\%$ , and  $> 6\%$ . The by-visit responses (based on the analysis visit windows described in [Table 3](#)) will be

assessed at the lumbar spine, total hip, and femoral neck. For the “all sites” analysis, subjects who have the pre-specified percentage BMD increase at all 3 anatomical sites at the same visit will be considered responders. A subject must have non-missing BMD results at all 3 anatomical sites at the same visit to be included in the “all sites” analysis. No imputation of missing data will be implemented. For the “all sites” analysis, the BMD response status at end of study will also be summarized. In this analysis, the “all sites” response status will be based on the subject’s last BMD assessment during the study. If the last BMD assessment is missing the result for one or two anatomical site(s), the subject will be classified as a non-responder at End of Study. The denominator for the percentage of BMD responders at End of Study will be the number of subjects in the analysis population who had both a baseline and a post-baseline BMD.

BMD responder analyses will also be performed at each of the 3 anatomical sites separately, using the same 3 categories of BMD response used in the “all sites” analysis. A subject must have non-missing BMD results at a given visit to be included in the by-visit analysis. No imputation of missing BMD data will be implemented.

The primary time point for all BMD responder analyses is Month 12. The 95% CI of the response rate in each treatment group will be provided using Wilson’s method. The Pearson chi-square test and 95% CI using a normal approximation will be used to explore the difference in the number (%) of responders between the 2 treatment groups at each visit (Months 3, 6 and 12) for each category of response. If the number of responders is less than 5 in any treatment group, the Fisher’s exact test will be used. No multiplicity adjustment to the p-values for the BMD responder analysis will be implemented.

#### **4.4.5.2. Time to Clinical Fracture**

Analysis of the time to new clinical fracture by Month 12 will be performed for exploratory purposes. Duration in days from the date of randomization to the first incidence of clinical fracture will be derived.

The crude incidence rates, Kaplan-Meier estimates of the incidence rate at Month 12, hazard ratio (95% CI) based on a Cox proportional hazard model without covariates, and Kaplan-Meier curves, and p-values from the log-rank test for the comparison of the treatment groups will be generated for this time-to-event variable.

If a subject does not experience any clinical fracture over the 12 months of treatment plus the 30-day follow-up, this subject will be censored at the last known day in the study up to the follow-up visit.

#### **4.4.5.3. Changes in Disease Status**

Disease status categories are:

- Osteoporosis, defined as lumbar spine or total hip BMD T-score  $\leq -2.5$
- Osteopenia, defined as:
  - lumbar spine T-score  $> -2.5$  and total hip BMD T-score  $> -2.5$  and  $< -1.0$ , or
  - lumbar spine T-score  $> -2.5$  and  $< -1.0$  and total hip BMD T-score  $> -2.5$
- Normal, defined as lumbar spine T-score  $\geq -1.0$  and total hip BMD T-score  $\geq -1.0$

The number and percentage of subjects for whom disease status has changed from osteoporosis at baseline to osteopenia, normal, or no change at end of study will be tabulated and analyzed using the CMH test stratified by baseline disease status. No imputation of missing BMD data will be implemented.

#### **4.5. Population Pharmacokinetics (PK)**

PK data will be analyzed and reported separately. Details of the PK data summaries and analysis methods will be provided in a separate analysis plan.

## **4.6. Safety Analyses**

All safety and tolerability analyses will be conducted using the Safety population, except the summary of TEAE by ADA status, which will be conducted using the Antibody population. Treatment classification will be based on the actual treatment received. Unless otherwise specified, no formal statistical hypothesis testing will be performed for safety endpoints, and the presentations will be based on descriptive summaries. For summaries involving visit, the nominal visit will be used, unless otherwise specified.

The impact of the COVID-19 pandemic and the implementation of a variety of mitigations for study conduct will be reviewed and evaluated carefully for the safety assessment. The pandemic-related protocol deviations including missed or delayed visits, missed safety related tests, use of alternative assessment procedures for visit execution, use of alternative data collection or alternative modalities, use of rescue medications, or non-adherence to the planned course of treatment will be identified. Additional data summaries and analyses addressing the impact of the pandemic may be performed if necessary.

### **4.6.1. Adverse Events**

All AEs will be coded to SOC and PT using MedDRA Version 24.0.

Analyses of AEs will be performed for those events that are considered to be TEAEs. A TEAE is defined as any AE that was absent (i.e., had not occurred) or had resolved prior to the start of study drug, and which occurred on or after the date of the first dose of study drug and within 30 days of the last dose of study drug; or any AE that started prior to the first dose of study drug, was ongoing after study treatment started, and increased in severity after the start of study drug and within 30 days of the last dose of study drug. AEs with missing onset dates will be handled according to the Conventions for Imputing Missing Dates in [Appendix A](#).

TEAEs reported as unanticipated adverse device effects (UADE) or medical device reports (MDR) are those AEs with “Yes” to all of the following three questions on the AE eCRF: “Serious Event?”, “Was AE related to device?”, and “Would you consider this AE unexpected?”. For North American sites, unanticipated device-related SAEs will be reported as UADE for abaloparatide-sMTS, and will be reported as MDR for subjects on abaloparatide-SC. For European sites, unanticipated device-related SAEs will be reported as UADE for subjects on either abaloparatide-sMTS or abaloparatide-SC.

In any tabulation of TEAEs, a subject contributes only once to the count for a given PT and/or SOC, or for a time period category. For summaries by severity, a subject with multiple occurrences of a TEAE will be represented under the most severe occurrence. For summaries by relationship to study drug, a subject with multiple occurrences of a TEAE will be represented under the most related occurrence.

An overall summary of AEs will be presented by treatment group and overall, including the number and percentage of subjects reporting AEs, TEAEs, study treatment-related TEAEs (with probable or possible relationship to study drug), severe TEAEs, treatment-related severe TEAEs, serious TEAEs, treatment-related serious TEAEs, TEAEs leading to study drug interruption, TEAEs leading to study drug withdrawal, TEAEs leading to discontinuation from study, TEAEs related to the device, and TEAEs resulting in death.

The following summaries will be presented:

- TEAEs by SOC and PT
- TEAEs by SOC, PT, and region (North America, Europe)
- TEAEs by SOC, PT and Maximum Severity (mild, moderate, or severe)
- TEAEs by SOC, PT and relationship to the study drug (related or not related)
- TEAEs by PT

*Note: which will be sorted in descending order of total number of subjects with the preferred term in the overall column.*

- Treatment-related TEAEs by SOC and PT
- Most Common ( $\geq 5\%$  in either treatment group) TEAEs by SOC and PT
- Severe TEAEs by SOC and PT
- Treatment-related Severe TEAEs by SOC and PT
- Serious TEAEs by SOC and PT
- Treatment-related Serious TEAEs by SOC and PT
- TEAEs leading to study drug withdrawal by SOC and PT
- TEAEs leading to discontinuation from study by SOC and PT
- TEAEs leading to death by SOC and PT
- TEAEs leading to study drug interruption by SOC and PT
- Non-TEAEs by SOC and PT.

SOCs will be sorted in alphabetical order. Within an SOC, AEs will be sorted in descending order of the total number of subjects with the PT in the overall group.

To explore the relationship between TEAEs and the duration of study drug exposure, the incidence of TEAEs by time of onset will be presented for the following categories:  $\leq 1$  month,  $> 1$  to  $\leq 3$  months,  $> 3$  to  $\leq 6$  months,  $> 6$  to  $\leq 9$  months, and  $> 9$  months, by treatment group, SOC, and PT. Subjects with multiple occurrences of an AE within a time period will be counted once in each time period that an onset of the AE occurs.

To evaluate the relationship between TEAEs and antibody status, the incidence of TEAEs will also be summarized by antibody status (ADA-, ADA+/Nab+, ADA+/Nab-, All ADA+, and Overall), SOC, and PT using the Antibody population. A summary of TEAEs by PT and antibody status will also be presented by treatment group, in which TEAEs will be sorted in descending order of total number of subjects with the preferred term.

To explore the effect of the COVID-19 pandemic on reported AEs, summaries of TEAEs by SOC and PT, TEAEs leading to treatment discontinuation, and serious TEAEs will also be presented:

- by AE onset date (AE occurs before 01 March 2020, vs AE occurs on or after 01 March 2020)
- by region (North America and Europe)

All TEAE summaries, including AEs of special interest (AESI, [Section 4.6.2](#)) will be presented by patch type (ultra-low bioburden, sterile) for the abaloparatide-sMTS group. The exposure-adjusted incidence rate of TEAEs will also be presented by patch type for the abaloparatide-sMTS group. The exposure-adjusted incidence rate is calculated as number of subjects with TEAEs divided by the total on-treatment exposure in subject-years.

The number of subjects with any TEAEs, the number of subjects with any SAEs, and the number of subjects with TEAEs leading to study drug withdrawal will also be summarized by treatment group, SOC, PT and age group (< 65, 65 - < 75, and  $\geq$  75 years). Similar tables will be provided by treatment group, SOC, PT and BMI group (BMI < 25, 25  $\leq$  BMI < 30, BMI  $\geq$  30). Both summaries by age group and by BMI group will also be presented by patch type (ultra-low bioburden, sterile) for the abaloparatide-sMTS group.

By-subject listings will be provided for all AEs, including an indicator for TEAE/non-TEAE and for patch type (ultra-low bioburden, sterile). Listings will also be provided for deaths, serious TEAEs, TEAEs leading to study drug withdrawal, TEAEs leading to discontinuation from study, AEs of special interest, and severe AEs.

A data listing for COVID-19 related AEs (AE PTs related to COVID-19 using MedDRA Version 24.0) will be prepared by SOC and PT. A listing of subjects who experience an UADE or MDR will be provided from the clinical database.

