7.1.4.2. Medical Device Reporting for Abaloparatide-SC

Sites will report medical device reports (MDRs) that reasonably suggest that abaloparatide-SC may have caused or contributed to a death or serious injury or has malfunctioned and the malfunction of the device would be likely to cause or contribute to a death or serious injury if the malfunction were to recur, including events occurring as a result of device failure, malfunction, improper or inadequate design, manufacture, labeling, or user error.

A serious injury is an injury or illness that:

- Is life threatening
- Results in permanent impairment of a body function or permanent damage to a body structure
- Necessitates medical or surgical intervention to preclude permanent impairment of a body function or permanent damage to a body structure

If the Investigator learns of any MDR after a subject has been discharged from the study, and such incident is reasonably related to abaloparatide-SC, the Investigator will promptly notify RADIUS.

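### SAP 4.6.1 identifies SC medical device reports with the UADE test, so its UADE/MDR listing omits expected serious events and malfunctions that the protocol defines as MDRs

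*SAP*

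**What the plan says.** **Protocol.** Section 7.1.4.2 covers the SC product. A report qualifies as an MDR if it reasonably suggests that "abaloparatide-SC may have caused or contributed to a death or serious injury or has malfunctioned"; for the second limb, the condition is that the device "has malfunctioned and the malfunction of the device would be likely to cause or contribute to a death or serious injury" on recurrence. Serious injury is given its own three criteria: a threat to life, permanent impairment or damage, or the need for intervention to prevent these. Section 7.1.4.1 defines the UADE for the sMTS device and makes lack of prior identification part of that definition. Section 7.1.6 keeps the terms apart by product (UADE for sMTS, MDR for SC), draws no distinction by region, and requires both to be entered in the eCRF within 24 hours of awareness. Section 8.4.4 plans a listing of UADEs only.

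**SAP.** Section 4.6.1 gives a single definition for "TEAEs reported as unanticipated adverse device effects (UADE) or medical device reports (MDR": a positive answer "to all of the following three questions on the AE eCRF". The questions concern seriousness, relation to the device, and expectedness ("Would you consider this AE unexpected"). Labels then depend on region. At North American sites an event that passes "will be reported as MDR for subjects on abaloparatide-SC". In Europe the label changes: "For European sites, unanticipated device-related SAEs will be reported as UADE for subjects on either abaloparatide-sMTS or abaloparatide-SC". The section ends with a planned listing of subjects with a UADE or MDR. No other definition of MDR is given in the SAP, and Section 5 does not list this one among the changes from the protocol.

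**The concern.** The SAP uses a protocol-defined term with a narrower meaning. It adds an unexpectedness condition that the protocol does not impose on MDRs. It works only from AE records, although the protocol's malfunction limb needs no harm to have occurred. It also gives European SC events a label that the protocol defines for the patch.

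What is at stake is how one listing in the study report is read. A reader who sees MDR will assume the protocol's meaning. A short or empty listing could then be taken to show that the pen had no reportable problems, when the rule had removed them.

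**Working it through.** No figure in the plan depends on this rule, so the check is a comparison of two definitions.

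- **Protocol MDR (7.1.4.2)** = [may have caused or contributed to death or serious injury] OR [malfunction likely to do so on recurrence]; SC product, any region.
- **SAP MDR (4.6.1)** = serious AND device-related AND unexpected, on an AE record; SC arm AND North American site.

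Four kinds of SC event can meet the protocol definition:

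| SC event | Protocol MDR | SAP, North America | SAP, Europe | Other planned SAP output |
|---|---|---|---|---|
| 1. Serious, device-related, unexpected AE | Yes | MDR | UADE | Serious TEAE tables and listing; device-related TEAE count; all-AE listing |
| 2. Serious, device-related, expected AE | Yes | Not captured | Not captured | Same as row 1 |
| 3. Qualifying malfunction, no AE | Yes | Not captured: no AE record on which to answer the questions | Not captured | None |
| 4. Qualifying malfunction with a non-serious AE | Yes | Not captured | Not captured | General TEAE tables; all-AE listing |

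Rows 1 and 2 assume that the event is a death or a serious injury in the protocol's sense.

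The SAP rule therefore captures 1 of 4 kinds, and in Europe labels 0 of 4 as MDR. These are kinds of event, not numbers of events.

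The two documents also use different notions of seriousness. The SAE criteria in Protocol 7.1.2 include hospitalization; the serious-injury criteria in 7.1.4.2 do not. An unexpected device-related hospitalization that met none of the three injury criteria and involved no qualifying malfunction would be an MDR under the SAP rule in North America but not under the protocol. Removing the expectedness question alone would therefore not reproduce the protocol's definition.

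**The case against.** The best defence is that little depends on the rule.

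- It feeds one by-subject listing. The MDR part of that listing is a SAP addition, since Protocol 8.4.4 plans only UADEs.
- The SAP's by-arm device measure is the count of TEAEs related to the device, in the overall AE summary (4.6.1) and again for AESIs (4.6.2). Neither applies the seriousness or expectedness filter.
- Site reporting within 24 hours follows the protocol definitions and is untouched.
- The same three questions apply to both arms, so the listing is at least like for like.

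All of this stands, and it rules out a stronger reading that a reader might reach: that SC device safety is under-counted across the study report and the comparison with the patch is distorted. The documents do not support that. No between-arm comparison of MDRs or UADEs is planned, and serious events excluded from the MDR label still appear in the serious-TEAE and all-AE outputs.

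It could also be said that the SAP sentence concerns only TEAEs, so malfunctions without an AE lie outside it. That accounts for row 3 but not for rows 2 and 4, which are AEs. It also leaves row 3 with no output, because the SAP offers no other route to an MDR. Nor can the narrowing pass as a declared choice: Section 5 describes everything it does not list as an enhancement of the protocol, and narrowing a defined term is a change.

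**Conclusion.** The definitions conflict, and the rule followed as written gives a UADE/MDR listing that is incomplete and partly mislabelled for SC. It omits expected serious device-related events, and qualifying malfunctions with no AE or only a non-serious one. Only malfunctions without an AE are absent from every planned SAP output; the rest lose the MDR label but are still reported.

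By-arm device-related TEAE counts, expedited reporting, the primary and secondary endpoints, the margin and the sample size are unaffected. The number of events involved cannot be estimated, because neither document gives a rate of pen malfunctions or of serious device-related events; it could be zero. The conclusion assumes that the listing is built from the 4.6.1 rule, the only MDR definition in the SAP. Label: wrong as written, minor.

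**What to change.** 1. Keep the three-question rule for UADE, for sMTS.
2. Define MDR in the SAP by direct reference to Protocol 7.1.4.2: no expectedness condition, the protocol's own serious-injury criteria instead of the SAE criteria, and malfunctions entered in the eCRF under 7.1.6.
3. Reconcile the European label for SC events with Protocol 7.1.4.1, 7.1.4.2 and 7.1.6, which have no regional split.
4. Record any difference that remains in SAP Section 5, with the reason.

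The cost is one more data source for one listing. Section 7.1.6 already sends MDRs to the eCRF, so that source should exist, though the documents do not say which form holds it. The drawback is that SC and sMTS entries in the listing will rest on different definitions, with a wider net for SC. A footnote should say so, so that the entries are not read as a comparison between arms.
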